BI IRB# 087-14 Acute and Short-Term Effects of CBD on Cue-Induced Craving in Drug-
Abstinent Heroin-Dependent Humans

NCT # 02539823

Version: March 12, 2017

The purpose of this study is to determine if Cannabidiol (CBD) - one of the natural components of the cannabis plant) is effective in reducing heroin craving. Current therapies available for heroin treatment such as methadone and buprenorphine, do not block heroin craving. Craving is a distressing symptom which is linked to relapse and ultimately the continued cycle of heroin abuse.

45 healthy male and female subjects between the ages of 21 and 65, who are currently abstinent from drug use but who have a recent history (past 3 months) of heroin-dependence will be recruited for the study. There will be 3 groups of 15 subjects. One group will receive a placebo (a solution that does not contain the experimental drug), 15 participants will receive 400 mg of Cannabidiol (CBD), and 15 participants will receive 800 mg of CBD. Dispensation of investigational drug will be randomized and double-blinded.

Participation in this research study will consist of 5 visits in total over a two week period, and will consist of one prescreening session (about 2 hours) and four test sessions. Test sessions 1, 2 and 4 include Cue sessions and will last 3 hours per visit. Test session 3 (no cue session) will last 90 minutes. The investigational drug (CBD) or placebo will be administered during test sessions 1, 2, and 3. There is a 1 week break between test session 3 and 4. There will be no CBD/placebo administration during test session 4.

The prescreening session will consist of:

- | Basic Physical exam
- | Toxicological assessments: urine drug screening including opioid metabolite screening and Breathalyzer. Positive findings will result in exclusion.
- | Urine pregnancy test, blood test (complete blood count, liver function tests, electrolytes, urea, creatinine, glucose), EKG, vital signs (heart rate, blood pressure, weight and height measurement, Body Mass Index calculation), survey of medical history (including tobacco use assessment). MD will determine medical eligibility based on physical exam and lab results.
- | Computerized Structured Clinical Interview for DSM-V (SCID-V) for diagnosing drug dependence. Participants must be positive for current dependence for heroin (within past 3 months), but must not be currently using any drugs (including heroin) besides nicotine.

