BI IRB# 087-14 Acute and Short-Term Effects of CBD on Cue-Induced Craving in
Drug- Abstinent Heroin-Dependent Humans

NCT # 02539823

Version: March 12, 2017

Statistical Analysis Plan

A linear mixed-model repeated-measures analysis using the SAS procedure MIXED (SAS Institute, Cary, N.C.) was employed to assess the changes in cue- induced in-clinic VAS-C, VAS-A, and PANAS scores. Changes in the Heroin Craving Questionnaire out-of-clinic craving scale score were assessed using a repeated-measures analysis conducted with the MIXED procedure. At the first stage of all analyses, the distributional characteristics of all continuous explanatory and outcome variables were assessed using skewness and kurtosis indicators. If necessary, transformations were used to normalize a variable. To determine the effectiveness of the randomization procedure for assignment to the drug group, one-way analyses of variance were conducted on the session 1 baseline values of each of the outcome variables as a function of drug group. Nonsignificant drug group baseline differences were taken as indicators of effective randomization. Because a crossover design assumes that there are no carryover effects from one assessment period to the next, this possibility was tested using procedures in the Number Cruncher Statistical System User's Guide II. Once the analyses indicated that carryover effects were absent, the main analyses of the crossover design variables were undertaken.

Difference scores between the precue baseline scores and postcue scores within each session were calculated and used as outcomes in the analytic models. The models themselves were developed sequentially in which time was entered first (because there were multiple sessions and two events within each session for the crossover outcomes; that is, neutral and drug cues). This procedure was followed by entering the variable describing the sequence in which the drug and neutral cues were given, the drug group variable, and the cue indicator (neutral or drug cue). A single first-order interaction term (drug group by cue) was entered last because it was hypothesized that the cues would be responded to differentially depending on the drug group to which the research participant was assigned. Any significant mean differences for the main effect analyses or interaction terms were followed up by Tukey-adjusted post hoc mean comparisons.

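### No scale or model term is named as primary, and Tukey protects only within one term on one scale, so false positives can accumulate across scales and terms

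*SAP*

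**What the plan says.** The SAP's first paragraph applies a mixed model to "in-clinic VAS-C, VAS-A, and PANAS scores". It then handles a fourth outcome separately: "Changes in the Heroin Craving Questionnaire out-of-clinic craving scale score were assessed". The second paragraph defines the in-clinic outcomes as change from before to after the cue ("Difference scores between the precue baseline scores and postcue scores within each session were calculated and used as outcomes"). It builds each model in steps: time, cue sequence, drug group, cue and, last, the interaction. On that interaction it says: "A single first-order interaction term (drug group by cue) was entered last because it was hypothesized".

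The paragraph closes with the only multiplicity provision in either document: "Any significant mean differences for the main effect analyses or interaction terms were followed up by Tukey-adjusted post hoc mean comparisons".

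The intended target can be partly inferred. The title is about "Effects of CBD on Cue-Induced Craving", and the protocol's opening paragraph asks whether CBD is "effective in reducing heroin craving". But neither document designates a primary scale or term, states a significance level, or sets an order of testing. The protocol's purpose does not choose between in-clinic and out-of-clinic craving, and the SAP analyses both.

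**The concern.** The follow-up rule is triggered by any significant term. Read literally, a drug-group or drug-group-by-cue result on any scale may be carried forward as evidence about CBD. Tukey limits error among the means compared within one term of one model. It does nothing about the number of scales or the number of terms tested.

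A smaller gap lies in the follow-up itself. The hypothesis is that the response to the cue depends on drug group, which is a difference of differences. The SAP lists no pairs. On the usual reading, Tukey compares pairs of the six group-by-cue means, and no such pair is a difference of differences. After a significant interaction, the plan would not show directly whether 400 mg or 800 mg changed the heroin-cue response more than the neutral-cue response, relative to placebo.

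At stake is whether a reader can tell which result tests the hypothesis, and how many chances the trial had to produce one.

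**Working it through.** The documents give no error rate, so there is no figure of theirs to reproduce.

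**Inputs**
- Three groups of 15 (protocol, opening section), so a one-way F test on 2 and 42 degrees of freedom.
- Three scales with a cue factor (SAP, first paragraph). The out-of-clinic questionnaire is taken to have a drug-group term but no cue term; its model is not listed.
- Assumed, because not stated: 0.05 per F test; equal correlation r between scales, from 0 to 0.9.

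**Step 1: the interaction F test on three scales.** If independent, the chance of at least one false positive is 1 − 0.95³ = 14.3%. Simulated under no CBD effect (200,000 runs per setting, F test on each person's heroin-minus-neutral difference):

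| r | 0 | 0.3 | 0.5 | 0.7 | 0.9 |
|---|---|---|---|---|---|
| At least one significant | 14.2% | 13.7% | 12.6% | 11.25% | 8.6% |

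**Step 2: add the Tukey step.** Same set-up, but now count a run only if the F test is significant and a Tukey-adjusted dose-versus-placebo difference follows on the same scale.
- Through the interaction, with Tukey over the 15 cell pairs and the difference taken under the heroin cue: under 1% of runs on any of the three scales (within-person cue correlation 0.3 to 0.7).
- Through the drug-group main effect, with Tukey over the three group means: about 6% to 10% of runs on any of the three scales.

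On one scale alone this two-step result cannot exceed 5%, because it requires an F test at 0.05. The 6% to 10% therefore comes from having three scales. Including the questionnaire cannot lower it.

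**Step 3: counting terms as well as scales.** One scale with both drug-group and interaction terms: 1 − 0.95² = 9.75%. Drug group on four scales plus interaction on three makes 7 F tests: 1 − 0.95⁷ = 30.2% if independent, and 23.2% by simulation at r = 0.7. The simulated value treats the two terms as independent (true when the two cue cells have equal variance) and rests on the assumed questionnaire model.

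**Step 4: what the cell pairs contain.** Six cells give 6 × 5 / 2 = 15 pairs: 6 between groups under the same cue (4 of them dose versus placebo), 3 heroin versus neutral within a group, and 6 that mix group and cue. None is (heroin − neutral on a dose) − (heroin − neutral on placebo).

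**Step 5: precision of that contrast.** With equal variances and within-person correlation ρ between the two cue responses, its standard error relative to the heroin-cue pair is √(2(1 − ρ)): 1.41 at ρ = 0, 1.18 at 0.3, 1.00 at 0.5 and 0.77 at 0.7.

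**The case against.** The strongest reply is that a significant F test is not a CBD effect. A test on 2 degrees of freedom has no direction. It can be significant because a dose looks worse than placebo, or because only the two doses differ. The SAP does not stop there, and the Tukey step is real protection. This stands. A reader might take the 9% to 14% as the chance of declaring a false CBD effect, but Step 2 shows that it is not, for a dose difference under the heroin cue reached through the interaction. It remains the relevant figure only if a bare interaction test is reported as the finding. The reply does not cover the drug-group main effect, which the rule also follows up.

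A second reply is that 5% is not the plan's claim. This also stands. A reader might infer that the plan breaks a stated 5% level, but no level or family-wise claim appears in either document.

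A third is that the target is clear from the title, the purpose and the hypothesised interaction. This is largely fair. But an inferable target does not bind an analysis whose rule admits any term on any scale.

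A fourth is that the contrast is a matter of preference. In part it is. The interaction F test already addresses cue-specificity, and dose versus placebo under the heroin cue is a valid simple effect, already corrected for the pre-cue score. What is missing is a comparison that attributes the cue-specific effect to a dose.

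Finally, the SAP is in the past tense (for example, "the main analyses of the crossover design variables were undertaken"). A reader might infer that it was written with results in hand. Tense alone does not establish that, and the documents do not settle it.

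**Conclusion.** The point holds in a limited form. The plan has four scales, no primary scale or term, and a single adjustment that reaches neither across scales nor across terms. At an assumed 0.05 per test, about 9% to 14% of null trials would show at least one significant interaction test on the three in-clinic scales. After Tukey, a false dose-versus-placebo difference under the heroin cue arises through the interaction in under 1%, but through the drug-group main effect in about 6% to 10%. The main-effect route is thus where excess error survives the plan's own protection.

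These figures assume no CBD effect on any scale, equally correlated scales and a one-way simplification of the mixed model. The 23% to 30% for seven tests needs further assumptions (Step 3) and is only indicative. The missing cue-specific contrast is secondary, and no gain in power is claimed for it. For a 45-person study this is a change worth making, not a fatal flaw.

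**What to change.** 1. Name the drug-group-by-cue effect on the in-clinic craving score as the single primary test, and state its significance level. That score is taken here to be VAS-C, an abbreviation that neither document spells out. At 0.05, a single primary test has a 5% false-positive chance.
2. Follow it with two multiplicity-adjusted contrasts, 400 mg versus placebo and 800 mg versus placebo, each on heroin minus neutral; Dunnett would serve. Keep the Tukey cell comparisons and 400 mg versus 800 mg as secondary.
3. Make the drug-group main effect, VAS-A, PANAS and the out-of-clinic craving scale secondary, with Holm or fixed-order testing.
4. If results were already known when the SAP was written, label this ranking post hoc and report how many tests were made. A ranking chosen then does not control error and improves reporting only.

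The cost is SAP wording and two contrast statements, with no new data. There are downsides. The secondary scales no longer stand alone as proof of effect. The comparison between doses leaves the primary set. At the same critical value, the contrast is less precise than the heroin-cue pair when within-person correlation is below 0.5.
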